**COMPLIANCE STATEMENT:**

This clinical investigation will be conducted in accordance with this Clinical Investigation Plan (CIP), the Declaration of Helsinki, applicable Good Clinical Practices (GCP) and regulations (e.g., US 21 Code of Federal Regulations (CFR) Part 50, 21 CFR Part 56, 21 CFR Part 812 and OUS ISO14155:2020) and the appropriate local legislation(s). The most stringent requirements, guidelines or regulations must always be followed. The conduct of the clinical investigation will be approved by the appropriate Institutional Review Board (IRB)/Ethics Committee (EC) of the respective investigational site and by the applicable regulatory authorities.

## 1.0 INTRODUCTION

The JET Enhanced Thrombectomy intervention (JETi) Registry is a post-market study to collect real-world data on the safety, performance, and clinical benefits of the JETi™ Hydrodynamic Thrombectomy System^1 (JETi System) for the treatment of acute/subacute thrombosis in the peripheral vasculature.

The JETi System is a hydro-mechanical aspiration system designed to continuously aspirate thrombotic material into the catheter, where a high-pressure stream of saline within the catheter tip macerates the thrombus as it is aspirated, allowing the safe removal of thrombus material from the vessel while minimizing risk of distal embolization and hemolysis. The system is intended to remove/aspirate fluid and break-up soft emboli and thrombus from the peripheral vasculature and to subselectively infuse/deliver diagnostics or therapeutics with or without vessel occlusion.

Several published studies have shown that the JETi System is safe and effective in the peripheral vasculature. In a retrospective study of 18 consecutive patients with thrombus in the iliofemoral, axillosubclavian, and portal veins, mean thrombus reduction with JETi alone was 92%. Procedural success was 100%, and technical success with the JETi alone was 76%; 24% of procedures requiring subsequent catheter directed thrombolytics (CDT) overnight. One subsegmental pulmonary embolism (PE) event was reported. In another study, 30 patients with acute lower extremity deep vein thrombosis (DVT), including iliofemoral, iliofemoral, and femoropopliteal) were treated with the JETi System. Technical success was 93.3%, and mean thrombus removal was 74.0%. No major complications were observed. In a prospective pilot study conducted in 47 patients with thrombus in the iliofemoral or iliofemoral veins treated in a single session with the JETi System, unobstructed flow was reestablished in 87% of patients with no major adverse events through 30 days. In addition to these studies reporting on venous thromboses, a recent presentation by Dandu et al. reported on a retrospective review of 27 patients treated for acute lower extremity ischemia. The success rate of all interventions in which the JETi System was used was 85%.

The JETi Registry is the first Abbott-sponsored data collection on the JETi System. It is a prospective, single-arm, multicenter study registering approximately 280 subjects treated for thrombosis in the peripheral vasculature from approximately 30 sites globally. Subjects treated for arterial, venous, or arteriovenous thromboses, and subject diagnoses such as acute limb ischemia (ALI), chronic limb ischemia/chronic limb threatening ischemia (CLI/CTLI), peripheral artery disease (PAD), deep vein thrombosis (DVT), and others may be included. Subject participation will be through the 12-month post-

---

 The JETi™ Hydrodynamic Thrombectomy System (HTS) was previously branded as the JETi All-in-one (AIO) Peripheral Thrombectomy System. The term "JETi System" will be used throughout the protocol to refer to all commercial versions of the JETi System covered in the Registry.

procedure visit with data collection at baseline, during the procedure, discharge, 30-day, and 12-month visits.

This Registry will collect data on the use of the JETi System in the treatment of patients undergoing a percutaneous thrombectomy procedure for peripheral thrombosis. This Registry will be conducted in accordance with this CIP. All investigators involved in the conduct of the registry will be qualified by education, training, and experience to perform their tasks and this training will be documented appropriately.

## **2.0 CLINICAL INVESTIGATION OVERVIEW**

### **2.1 Clinical Investigation Objective**

The objective of the JETi Registry is to collect real-world data on the safety, performance, and clinical benefits of the JETi System for the treatment of thrombosis in the peripheral vasculature.

### **2.2 Device Used in the Clinical Investigation**

#### **2.2.1 JETi System**

This Registry may include any commercially available JETi System at participating sites.

#### **2.2.2 Indication for Use**

##### **JETi Hydrodynamic Thrombectomy System (JETi HTS) – US**

The JETi Hydrodynamic Thrombectomy System is intended to remove/aspirate fluid and break-up soft emboli and thrombus from the peripheral vasculature and to subselectively infuse/deliver diagnostics or therapeutics with or without vessel occlusion.

##### **JETi Peripheral Thrombectomy System – CE MDD**

The JETi Peripheral Thrombectomy System is intended to remove/aspirate fluid and break-up soft emboli and thrombus from the peripheral vasculature and to sub selectively infuse/deliver diagnostics or therapeutics.

The JETi Peripheral Thrombectomy System is intended to be used for less than 30 days.

#### **2.2.3 Description of the Device**

The JETi System is a hydro-mechanical aspiration system, intended for the removal of intravascular thrombus. The system is comprised of the JETi Catheter (6F or 8F), JETi Pump Set, JETi Saline Drive Unit (SDU), JETi Accessory Cart, JETi Suction tubing, and JETi Non-sterile Canister Set. The JETi System is designed to continuously aspirate thrombotic material into the catheter, where a high-pressure stream of saline within the catheter tip macerates the thrombus as it is aspirated. Further information can be found in the Instructions for Use (IFU) supplied with the SDU.

### 3.0 CLINICAL INVESTIGATION DESIGN

The JETi Registry is a prospective, single-arm, multicenter study to collect real-world data on the safety, performance, and clinical benefits of the JETi System for the treatment of acute and subacute thrombosis in the peripheral vasculature. This is a post-market study that will register approximately 280 subjects at approximately 30 centers globally. Subjects participating in this registry will be followed through their 12-month follow up visit.

After JETi procedure, subjects will be evaluated at discharge, 30 days, and 12 months.

The Sponsor has designed this study to involve as little pain, discomfort, fear, and any other foreseeable risks as possible for subjects. Refer to the Risks Analysis section (**Section 15.0**) of this clinical investigation plan for details.

[figure not shown]
#### 3.1 **Clinical Investigation Procedures and Follow-up Schedule**

The study flowchart is shown in **Figure 1**, and the follow-up requirements are described in this Section. After meeting all eligibility criteria, a subject is considered enrolled in the registry from the moment the subject provides written informed consent. The point of registration in the registry is when a JETi Catheter is introduced into the intended vasculature of an enrolled subject during the procedure (Day 0). A subject who is enrolled but not registered in this study will be considered a screen failure. Consenting up to 5 days after the JETi procedure is acceptable. In these cases, the point of registration will be the same and any procedural information will be entered post-consent, and adverse events (AEs) will be collected retrospectively from the point of registration (Day 0). Any assessments performed prior to consent will be conducted per standard of care and data collection will occur after consent is obtained. Any assessment performed after consent will be conducted per the protocol's requirements. Registered subjects' data will be collected at baseline, procedure, and discharge, as well as at 30 days (-20 days/+30 days), and 12 months (-5 months/+1 month) after the JETi procedure.

For all follow-up visits, if all attempts to have the patient return to the office for an in-office visit are unsuccessful, a phone call or virtual follow-up will be allowed to collect available data. Protocol deviations must be reported for data that could not be collected via phone.

Refer to the detailed follow-up schedules in **Section 6.1.6** and **6.2.6**.

Figure 1: Study Flowchart

\*Consenting up to 5 days after the JETi procedure is acceptable.

### 3.2 Measures Taken to Avoid and Minimize Bias

An independent core laboratory will be used for imaging data analysis to minimize bias. All angiograms, venograms and duplex ultrasound (DUS) imaging will be sent to the core laboratory for analysis. See **Section 6.3** for details. In addition, a Clinical Events Committee (CEC) will be included for adjudication of safety events.

### 3.3 Suspension or Early Termination of the Clinical Investigation

The Sponsor reserves the right to discontinue the Registry at any stage or reduce the follow-up period with suitable written notice to the investigator. Should the Sponsor discontinue the Registry, sites will follow subjects per routine hospital practice with device-related AEs reported to the Sponsor as per vigilance/commercial reporting requirements. The investigator shall return all Registry materials to the Sponsor and provide a written statement to the IRB/ EC (if applicable). All applicable Registry documents shall be subject to the same retention policy as detailed in **Section 11.5** of the CIP.

If the Sponsor suspends or prematurely terminates the Registry at an individual site in the interest of safety, the Sponsor will inform all other Principal Investigators. If suspension or premature termination occurs, the Principal Investigator or authorized designee will promptly inform the registered subjects at his/her site, and patients will continue to be treated per site standard of care. A Principal Investigator, IRB/EC, or regulatory authority may also suspend or prematurely terminate participation in the Registry at the investigational site(s) for which they are responsible. The investigators will follow the requirements specified in the Clinical Trial Agreement.

## 4.0 ENDPOINTS

### 4.1 Primary Endpoints

#### 4.1.1 Arterial Subjects

For subjects treated for arterial thrombosis (may include diagnoses such as acute limb ischemia, chronic limb ischemia/chronic limb threatening ischemia, peripheral artery disease, etc.) or arteriovenous (AV graft, AV fistula) thrombosis, all endpoints are descriptive.

There will be no hypothesis testing, and there are no statistical power considerations. For subjects treated for arterial or arteriovenous thrombosis, the primary endpoints are:

- **Clot removal grade** for each JETi-treated target vessel(s) from pre-JETi angiogram to post-JETi angiogram (post-JETi thrombectomy and prior to any adjunctive therapies to treat underlying culprit lesions) per the grades in **Table 1** (vessel basis). The independent imaging core laboratory will be responsible for assessing this endpoint.
- **Composite of JETi-related major adverse events (MAEs)**, defined as the following JETi-related events: device-related death, major amputation of the treated limb (arterial subjects only),

or major bleeding up to 30 days post-JETi procedure and as adjudicated by a clinical events committee (CEC) (subject basis). Refer to **Appendix II** for definitions of major adverse events.

**Table 1. Clot Removal Grade**

Grade I	< 50% reduction
Grade II	50 - <95% reduction
Grade III	95 - 100% reduction

#### 4.1.2 Venous Subjects

For subjects treated for lower extremity DVT, the primary endpoints are:

- **Percent of treated vessel(s) with  $\geq 75\%$  venous thrombus reduction** from pre-JETi venogram to final venogram (post-JETi AND after any/all adjunctive therapies to treat underlying culprit lesions) via modified Marder score. The independent imaging core laboratory will be responsible for assessing this endpoint.  
If no adjunctive therapies or devices are used after JETi, post-JETi modified Marder score is also final score.

- **Composite of JETi-related major adverse events (MAEs) up to 30 days post-JETi procedure**, defined as the following JETi-related events adjudicated by a clinical event committee (CEC):
  - 1) death,
  - 2) symptomatic pulmonary embolism (PE),
  - 3) major bleeding
  - 4) re-thrombosis of JETi-treated vessel(s).Refer to **Appendix II** for definitions of major adverse events.

 Refer to Appendix II for definition of Lower Extremity Deep Venous Thrombosis

Note, the effectiveness outcome for subjects treated for venous thrombosis that is not lower extremity DVT as defined in **Appendix II** (e.g., upper extremity DVT) will be assessed by clot removal grade, as defined in **Section 4.1.1**.

## 4.2 Descriptive Endpoints

### 4.2.1 All Subjects:

- Procedure-related death as adjudicated by a CEC.
- JETi-related AEs collected at discharge, 30 days, and 12 months follow-up, and as adjudicated by a CEC.
- Procedure-related access site complications such as hematoma, pseudoaneurysm (false aneurysm), perforation, as adjudicated by a CEC.
- Treatment Used: The number and percentage of patients having each of the following treatments:
  - JETi mechanical thrombectomy only
  - JETi in combination with one or more of the following treatments:

- Short-Form Health Survey-12 (SF-12) at baseline, 30-day and 12-month follow-up.

### 4.2.2 Arterial Subjects

- Clot removal grade for each JETi-treated target vessel from pre-JETi angiogram to final angiogram (post-JETi thrombectomy and after any/all adjunctive therapies and prior to removal of the vascular sheath) per the grades in **Table 1**.
- Components of the MAE including device-related death, major amputation of treated limb (arterial subjects only), and major bleeding up to 30 days post-JETi as adjudicated by a CEC.
- Ankle Brachial Index\* (ABI) of treated limb(s) at baseline and 30 days.
- Rutherford\* classification at baseline and 30 days.  
*\* only applicable to subjects with lower limb arterial thrombus*
- Rate of re-thrombosis of JETi-treated vessel at 30 days, and 12 months, as assessed by investigator/physician reported.

- Patency as determined by duplex ultrasound at baseline 30-day, and 12-month follow-up. Note that this endpoint will only apply to subjects treated for arteriovenous thrombus.
- Vessel patency: assessed by the independent imaging core laboratory using the Modified Thrombolysis in Myocardial Infarction (TIMI) classification called TIPI (Thrombo-aspiration in Peripheral Ischemia) (Table 3) for each JETi-treated vessel, assessed using angiogram
  - At post-JETi timepoint (post-JETi thrombectomy and prior to any adjunctive therapies to treat underlying culprit lesions)
  - At final timepoint (post-JETi thrombectomy and after any/all adjunctive therapies and prior to removal of the vascular sheath)

If no adjunctive therapies or devices are used after JETi, post-JETi TIPI score is also final TIPI score.

**Table 3. Thrombo-aspiration in Peripheral Ischemia (TIPI)**

Description	TIPI score
No recanalization of the thrombotic occlusion	0
Incomplete or partial recanalization of the thrombotic occlusion with no distal flow	1
Incomplete or partial recanalization of the thrombotic occlusion with any distal flow	2
Complete recanalization of the thrombotic occlusion with normal distal flow	3

- Acute success, as per TIPI score (Table 3):
  - Device success: Near complete or complete recanalization of occluded vessel, defined as post-JETi TIPI 2-3.
  - Technical success: Near complete or complete recanalization of occluded vessel, defined as final TIPI 2-3, where final TIPI evaluation occurs after JETi system and any other adjunctive device or procedures.
  - Procedural success: Technical success with no JETi-related MAEs within 5 days of registration or by discharge, whichever occurs first.

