### **5.3.2 Inclusion Criteria**

#### **5.3.2.1 General Inclusion Criteria**

1. Subject was treated or is expected to be treated for acute/subacute thrombosis, as determined by the investigator, in the peripheral vasculature with the JETi Hydrodynamic Thrombectomy System.
2. Subject or legally authorized representative must provide written informed consent.
3. Subject must be  $\geq 18$  years of age.

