## 6.0 TREATMENT AND EVALUATION OF ENDPOINTS

For this Registry, the following definitions apply:

- **Index procedure:** the entire intervention to treat the subject's peripheral vascular thrombosis. A subject's procedure may include more than one session if the subject is removed from the interventional suite and placed in a holding area with the intention of returning to the suite for additional treatments either the same day or following day (e.g., catheter placement or removal for CDT). An index procedure can start with JETi or any other treatment first.
- **Treatment:** the individual techniques performed during a procedure to address the subject's peripheral vascular thrombosis (e.g., JETi thrombectomy, balloon angioplasty, stent placement, or catheter-directed thrombolysis (CDT)). Note that "JETi treatment" will refer to treatment during which the JETi Thrombectomy device is used.

NOTE: A subject's treatment is determined by the treating physician based on the clinical situation and institutional practices.

- **Session:** a session is the in and out period within an interventional suite that a subject is receiving treatment. A subject's procedure may include more than one session if the subject is removed from the interventional suite and placed in a holding area with the intention of returning to the suite for additional treatments either the same day or following day (e.g., catheter placement or removal for CDT).

---

 Specifically Lower Extremity DVT subjects as defined in Appendix II

NOTE: Treatment for unexpected re-thrombosis is an adverse event and should not be considered as an additional session of the initial procedure.

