1.4.2.2 Arterial Subjects

- Clot removal grade for each JETi-treated target vessel from pre-JETi angiogram to final
 angiogram (post-JETi thrombectomy and after any/all adjunctive therapies and prior to removal of
 the vascular sheath) per the grades in Table 1.
- Components of the MAE including device-related death, major amputation of treated limb (arterial subjects only), and major bleeding up to 30 days post-JETi as adjudicated by a CEC.
- Ankle Brachial Index* (ABI) of treated limb(s) at baseline and 30 days.
- Rutherford* classification at baseline and 30 days.
 * only applicable to subjects with lower limb arterial thrombus.
- Rate of re-thrombosis of JETi-treated vessel at 30 days, and 12 months, as assessed by investigator/physician reported.
- Patency as determined by duplex ultrasound at baseline, 30-day, and 12-month follow-up. Note that this endpoint will only apply to subjects treated for arteriovenous thrombus.
- Vessel patency: assessed by the independent imaging core laboratory using the Modified Thrombolysis in Myocardial Infarction (TIMI) classification called TIPI (Thrombo-aspiration in Peripheral Ischemia)¹ (Table 3) for each JETi-treated vessel, assessed using angiogram.
 - At post-JETi timepoint (post-JETi thrombectomy and prior to any adjunctive therapies to treat underlying culprit lesions)
 - At final timepoint (post-JETi thrombectomy and after any/all adjunctive therapies and prior to removal of the vascular sheath)

¹ de Donato G, Pasqui E, Sponza M, et al. Safety and Efficacy of Vacuum Assisted Thrombo-Aspiration in Patients with Acute Lower Limb Ischaemia: The INDIAN Trial. *Eur J Vasc Endovasc Surg*. 2021;61(5):820-828. doi:10.1016/j.ejvs.2021.01.004

Statistical Analysis Plan

If no adjunctive therapies or devices are used after JETi, post-JETi TIPI score is also final TIPI score.

Table 3. Thrombo-aspiration in Peripheral Ischemia (TIPI)

Description	TIPI score
No recanalization of the thrombotic occlusion	0
Incomplete or partial recanalization of the thrombotic occlusion with no distal flow	1
Incomplete or partial recanalization of the thrombotic occlusion with any distal flow	2
Complete recanalization of the thrombotic occlusion with normal distal flow	3

- Acute success, as per TIPI score (Table 3), per core lab assessment:
 - Device success: Near complete or complete recanalization of occluded vessel, defined as post-JETi TIPI 2-3.

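### Arterial device success is a post-JETi TIPI score with no pre-JETi reading, so a vessel that already had distal flow can be counted as a success without any JETi effect

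*Protocol*

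**What the plan says.** **Success rules.** Protocol 4.2.2, beneath the TIPI table, gives "Device success: Near complete or complete recanalization of occluded vessel, defined as post-JETi TIPI 2-3". Technical success uses the same cut on the last image, "defined as final TIPI 2-3, where final TIPI evaluation occurs after JETi system and any other adjunctive device or procedures". Procedural success is technical success without an early JETi-related MAE. Protocol 6.1.2 repeats the three rules. SAP 1.4.2.2 has the same device rule, "Device success: Near complete or complete recanalization of occluded vessel, defined as post-JETi" TIPI 2-3.

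**Time points.** Protocol 4.2.2 and SAP 1.4.2.2 list two TIPI readings for each JETi-treated vessel. One is "At post-JETi timepoint (post-JETi thrombectomy and prior to any adjunctive therapies to treat underlying culprit lesions"; the other is taken at the end of the procedure. A pre-JETi reading is not listed.

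**Scale.** TIPI 2, the lowest score that counts as success, is "Incomplete or partial recanalization of the thrombotic occlusion with any distal flow". TIPI 0 is "No recanalization of the thrombotic occlusion".

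**Who and what can enter.** Protocol 5.3.2.1 asks that "Subject was treated or is expected to be treated for acute/subacute thrombosis, as determined by the investigator, in the peripheral vasculature" with JETi; occlusion or absent flow is not a condition. Protocol 4.1.1 makes the arterial group broad: acute and chronic limb ischemia, peripheral artery disease, and AV graft or fistula thrombosis. Under Protocol 6.0, "An index procedure can start with JETi or any other treatment first".

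**Pre-JETi image.** Protocol 6.1.2 and Table 5 require a pre-JETi angiogram, and Protocol 6.1 asks that angiograms go to the core laboratory. Its stated use is to show the initial clot burden.

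**The concern.** A rate called device success should describe what the device did. Here the rule looks only at flow after JETi. Distal flow may already be present before JETi, either because the thrombus did not fully block the vessel or because an earlier treatment in the same index procedure reopened it. Such a vessel can satisfy the rule with no contribution from JETi.

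The registry has no comparator and no test for arterial subjects, so the definition alone gives the number its meaning. If vessels with prior flow are counted, the rate rises with their share in the case mix. It then cannot be read as recanalization of occluded vessels by JETi, nor compared across sites or series with a different share.

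**Working it through.** **1. Is there a starting state?** The arterial measures compare as follows (Protocol 4.1.1, 4.2.2; SAP 1.4.1.1, 1.4.2.2).

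| Measure | Start | End |
|---|---|---|
| Clot removal grade (primary) | pre-JETi angiogram | post-JETi angiogram |
| Clot removal grade (descriptive) | pre-JETi angiogram | final angiogram |
| ABI, Rutherford | baseline | 30 days |
| Device success | none stated | post-JETi TIPI |
| Technical success | none stated | final TIPI |

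Only the TIPI-based successes lack a starting value. Procedural success is built on technical success and shares the gap.

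**2. Can a vessel with flow reach the numerator?** TIPI is scored in every JETi-treated vessel. Eligibility does not require occlusion, treatment may precede JETi, and TIPI 2 needs only partial recanalization with any distal flow. No text excludes a non-occluded vessel from the denominator or says how to score it. So it can.

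**3. Size.** The documents give no arterial success rate to reproduce and no share of vessels with prior flow. What follows is an illustration on assumed values.

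- b = share of treated vessels with distal flow before JETi, all taken to keep it and to be scored 2-3
- r = share of the remaining vessels in which JETi restores flow
- Reported rate = b + (1 - b)r
- Excess over r = b + (1 - b)r - r = b(1 - r)

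| r | b = 10% | b = 20% | b = 30% | b = 40% |
|---|---|---|---|---|
| 50% | 55% | 60% | 65% | 70% |
| 70% | 73% | 76% | 79% | 82% |
| 85% | 86.5% | 88% | 89.5% | 91% |

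For example, with r = 70% and b = 30%: 0.30 + 0.70 × 0.70 = 0.79, an excess of 0.30 × 0.30 = 9 points. At r = 0 the reported rate equals b.

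If only a fraction k of the vessels with prior flow keep it, the rate is bk + (1 - b)r and the excess is b(k - r), still upward while k is above r.

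**4. Read backwards.** A reported 85% would imply r = (0.85 - b)/(1 - b):

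- b = 10%: 0.75/0.90 = 83.3%
- b = 20%: 0.65/0.80 = 81.3%
- b = 30%: 0.55/0.70 = 78.6%
- b = 40%: 0.45/0.60 = 75.0%

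**The case against.** **The wording may already limit the scope.** Every TIPI level is phrased as recanalization of a thrombotic occlusion, and the success labels speak of an occluded vessel. On a literal reading, a vessel in which nothing changed has no recanalization and scores 0, or a non-occluded vessel is outside the endpoint. A reader might infer that every vessel with prior flow is an automatic success; the documents do not establish that. They do not prevent it either. With r = 70% and b = 20%, excluding those vessels gives 70% and scoring them 2 gives 76%. Scoring them 0 gives 0.80 × 0.70 = 56%. The rate depends on a rule that is not written.

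**A pre-JETi TIPI may exist in practice.** Protocol 6.1.2 lists three arteriograms and then says treated arterial vessels receive TIPI grades, without naming a time point. Core laboratory guidelines are provided separately and are not available here. This is fair, but no success definition in either document uses such a reading.

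**The question is answered elsewhere.** The primary arterial endpoint starts from the pre-JETi angiogram, so a vessel that JETi left unchanged is Grade I there. Treatments are recorded in order, so vessels treated before JETi can be identified. The TIPI endpoints are descriptive, without test or power. All of this stands and limits the impact.

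**Technical success is different.** A reader might infer that technical and procedural success need the same restriction. They do not: both credit the whole procedure, including other devices. Limiting them to pre-JETi TIPI 0-1 would wrongly drop vessels that were occluded when the index procedure began and were opened by an earlier treatment.

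**Conclusion.** The concern holds for device success, as a possibility that the definition leaves open. A vessel with distal flow before JETi can be counted as a device success with no JETi effect, because no pre-JETi TIPI is listed and nothing makes the reference to an occluded vessel operative.

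If such vessels are counted and keep their flow, the descriptive rate is too high by b(1 - r). At an assumed r of 70%, that is 3 points at b = 10%, 6 at 20% and 12 at 40%. Both b and r are assumptions, so these figures show scale only. They are not evidence that the registry's rate is biased by any given amount.

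The consequence is confined to a secondary descriptive measure; the primary arterial endpoint is unaffected. The change is still worth making, because the image needed is already collected and the measure carries the name device success.

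**What to change.** In Protocol 4.2.2 and 6.1.2 and SAP 1.4.2.2:

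- Add a pre-JETi TIPI, scored by the core laboratory on the pre-JETi angiogram. Where another treatment came first, state whether that image is taken before or after it; for device success it should show the state immediately before JETi.
- Define device success among vessels with pre-JETi TIPI 0-1 as progression to post-JETi TIPI 2-3, and state the denominator.
- Report vessels with pre-JETi TIPI 2-3 separately, with a shift table of pre-JETi, post-JETi and final TIPI. Improvement from 2 to 3 then stays visible.
- Keep technical and procedural success as defined, but present them by pre-JETi TIPI and by whether another treatment preceded JETi.

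The cost is one extra score per vessel on an existing image, plus Protocol and SAP wording. No visit, image or patient burden is added, and images already submitted could be re-read. The downside is a smaller device-success denominator, hence less precision, and possibly a lower reported rate.
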